#### **Research Design and Methodology**

The overall goal of this study is to use findings from Phase 1 (See protocol number 2020-0017) to deliver and refine a tailored ESD violence prevention training for diverse trans women. Participants for Phase 2 (n = 48) will be recruited from online forums including social media sites (e.g., Facebook, Twitter), banner ads on social networking/dating sites (e.g., Scruff, BGC Live, OK Cupid, Lex) that are trans-inclusive and through dissemination of paper and/or electronic recruitment flyers with leaders of community organizations that connect transgender individuals (e.g., AVP; Callen Lorde, Trans-lantinx network). Participants from prior studies who consented to future contact will be sent the study flyer by email. The proposed curriculum will be systematically refined based on delivery of the intervention to 3 groups of 16 TW each in a 20-hour training program, in 5 4-hour sessions. We have contracted with Prepare, Inc., the New York City chapter of IMPACT International to deliver the tailored ESD violence prevention intervention. IMPACT is an international ESD violence prevention organization with chapters across the United States. Prepare, Inc. will provide facilitators who have completed IMPACT's nationally standardized ESD violence prevention program requirements that include receipt of over 100 hours of training. IMPACT training is open to trans and cisgender women. The extensive training of IMPACT facilitators promotes intervention efficacy, while the risk of potential bias conferred by their experience with a pre-existing curriculum is mitigated by our community-engaged approach (i.e., TW community members, service providers, and scientists [PI and Co-I] collectively shape the content of the final tailored ESD intervention, and TW co-facilitators will be present in every training session). Prior to the start of group, facilitators will review the tailored curriculum in detail and attend 2-3 supervision/training meetings with the PI. These meetings will consist of reviewing the curriculum, role-plays of critical intervention components, and discussion of questions or concerns. The primary outcome of Aim 2 is to evaluate our ability to recruit our target (n = 48) and retain >75% over the course of the intervention. Successful completion of the pilot trial, including meeting or exceeding these benchmarks for success, will determine the feasibility and acceptability of recruiting participants into a future RCT. Preliminary efficacy of the tailored ESD violence prevention intervention will be evaluated as an exploratory aim. Participants enrolled in the pilot trial will be administered a battery of validated baseline questionnaires at baseline, immediately following the course, and 6 months after course completion (see Assessment Packet in attached below) including: - Demographics - Social Class Ladder- Community Ladder- Service Utilization Form - Sexual experiences Survey - Everyday Discrimination

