**Initial Application** 

**[name]** 

## 6. Research Design - Procedures and Risks

Participant Group	
List all research related procedures/data collection methods involving interaction or intervention with participants; use the Add New Procedure and Risk button to add each method.	List all research related procedures/data collection methods involving interaction or intervention with participants; use the Add New Procedure and Risk button to add each method.
Procedure	Self-Report Questionnaires
Where it will take place?	Self-report questionnaires will be administered virtually. Participants will have the option to complete baseline and course follow-up surveys remotely at home, or using iPads or their phones at God's Love We Deliver before and after the course.
When it will take place?	Self-report questionnaires will be administered to each participant 3 times; baseline (before the ESD intervention), follow-up directly after the intervention, and 6-month follow-up.
Frequency	Self-report questionnaires will be administered to each participant 3 times; baseline, follow-up immediately following course completion, and 6-month follow-up.
Is procedure optional for participants?	Yes
Associated risk or discomfort	Questionnaires include some questions concerning personal or emotional matters that could cause mild, temporary psychological discomfort.
Anticipated severity of risk or discomfort	No more than minimal risk
Expected frequency of risk or discomfort	Self-report questionnaires will be administered to each participant 3 times; baseline, follow-up immediately following course completion, and 6-month follow-up.
Risk reduction or mitigation method	While every possible step will be taken to minimize such risk, if participants have any concerns about any aspect of the study, consent documentation will make it clear that they may refuse to continue with the study at any time, without penalty. In addition, we will remind participants during the course of all assessments that they do not have to respond to any questions they do not wish to and may discontinue participation at any time. Participants who report or demonstrate any distress during study assessments will be referred to counseling services at local agency with whom the PI has established linkages (The Center). All counseling resources are available to

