When it will take place?	Exit Interviews will be scheduled on the fifth and final session of the course, and will take place in the weeks immediately following the course.
Frequency	Each participant will be interviewed once.
Is procedure optional for participants?	Yes
Associated risk or discomfort	No risk is expected from the exit interview questions.
Anticipated severity of risk or discomfort	No more than minimal risk

Expected frequency of risk or discomfort	No risk is expected from the course assessment questions.
Risk reduction or mitigation method	While every possible step will be taken to minimize such risk, if participants have any concerns about any aspect of the study, consent documentation will make it clear that they may refuse to continue with the study at any time, without penalty. In addition, we will remind participants during the course of all assessments that they do not have to respond to any questions they do not wish to and may discontinue participation at any time. Participants who report or demonstrate any distress during study assessments will be referred to counseling services at local agency with whom the PI has established linkages. All counseling resources are available to participants regardless of ability to pay.

Page 14 of 36

2021-0291

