## DSMB?s prospectively identified criteria for discontinuing the study

Adverse Event (AE): Defined as any untoward medical occurrence in a patient or research subject administered a pharmaceutical product or other research intervention and that does not necessarily have a causal relationship with this treatment. An AE can therefore be any unfavorable and unintended sign (including an abnormal laboratory finding), symptom, or disease temporally associated with the use of a medicinal (investigational) product or research procedure, whether or not related to the medicinal (investigational) product or procedure. Negative events that occur during study involvement do not constitute adverse events unless they lead to physical harm (in which case the injury is the AE) or deterioration of mental health functioning (in which case the symptoms are the AE). Negative events that may potentially affect response to the intervention or study involvement should be reported as AEs. See IRB Reporting Requirements below for instructions on how to report these events. Examples might include legal problems or traumatic events. The program facilitator should query about adverse events (AEs) at every session by asking about any notable events since the last visit. These should be reviewed in a timely manner with the supervisor. Serious Adverse Event (SAE): An AE occurring in a patient or subject enrolled in a research study is serious if it results in any of the following outcomes: death, a life-threatening adverse drug experience, inpatient hospitalization or prolongation of existing hospitalization, a persistent or significant disability/incapacity, or is a congenital anomaly/birth defect.Unanticipated Problems Involving Risk (UPR): Defined as being (1) unexpected given the research procedures and characteristics of the population, (2) related (or possibly related) to participation in the research and (3) indicative that the research may place the subject or others at a greater risk of harm than was previously known. Examples of possible UPRs for psychotherapeutic interventions: 1. Psychosis or mania2. New onset or clinically significant exacerbation of a psychiatric disorder3. Suicide and suicide attemptsAn incident, experience, or outcome that meets UPR criteria generally will warrant consideration of substantive changes in the research protocol or informed consent process/document or other corrective actions in order to protect the safety, welfare, or rights of subjects or others. Examples of corrective actions or substantive changes that might need to be considered in response to an unanticipated problem include: modification of inclusion or exclusion criteria to mitigate the newly identified risks; implementation of additional procedures for monitoring subjects; suspension of enrollment of new subjects;suspension of research procedures in currently enrolled subjects;modification of informed consent documents to include a description of newly recognized risks; and provision of additional information about newly recognized risks to previously enrolled subjects. Reporting Requirement: All UPRs/AEs/SAEs, regardless of relatedness to the intervention, are to be reported to the local IRB as soon as possible, no later than 10 business days from the date the investigator or research staff becomes aware of the event/problem. Fill out an AE form, SAE form, and/or UPR form, obtain the study PI's signature, and submit to the Hunter IRB. Then forward each AE/SAE/ UPR form to Data Safety Monitoring Board as soon as possible. The study PI will maintain a record of all AEs/SAEs/ UPRs to report to the Hunter IRB in summary or table form at the end of the study. The PI will notify NIMHD of any UPR, AE, or SAE promptly via email. Protocol Deviation/ViolationA protocol deviation or violation is any change, divergence, or departure from the study design or procedures of a research protocol. Investigators are required to conduct their research according to the plans reviewed and approved by the IRB. Instances where this does not occur, either inadvertently due to circumstances beyond the investigator's control, or due to errors of omission or commission by research project staff, must be reported. Reporting Requirement: Fill out a Protocol Deviation/ Violation form, and submit to local IRB within 3 days of the occurrence (one day if there was harm to the participant). Also email the form (with encryption) to the PI and Study Coordinator, who will maintain a record of all Protocol Deviations/Violations to report to the Hunter IRB.

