**Initial Application** 

## 16. Participants - Privacy and Confidentiality

# Describe the mechanisms in place to protect the privacy of participants during recruitment, consent process and research procedures

Strict confidentiality will be maintained and all data will be assigned a subject number. Participants will complete screening individually at a time most convenient for them. Screening procedures do not involve the collection of identifying information. If participant completes internet-based consent, participants identities will not be known to study staff until they have provided consent. If participant completes oral consent, no identifying information will be collected until oral consent is received. Strict confidentiality will be maintained and all data will be labeled using the participant's self-assigned ID. Participants will complete screening individually at a time most convenient for them. Screening procedures do not involve the collection of identifying information. Consent (if completed online) and self-report questionnaires will be self-administered by the participant at a time most convenient and comfortable for them. If participants opt to complete consent orally, a single member of the lab is responsible for guiding participants through the consenting process, and the member of the lab will complete this in a private space. The participant will complete baseline and follow-up self-report questionnaire batteries online at a time and place most comfortable to them, or on their personal device or lab iPad at God's Love We Deliver (before or after the first and last course sessions). The 6 month follow-up survey must be completed remotely. The institutional Zoom account of the PI will be used for video interviewing. Participants will receive a secure and private Zoom link to access the video interview, which will restrict access to any users other than the participant and the single member of the research staff responsible for administering the interview. Research staff will conduct the video interview in a private room, and the participant will have the ability to participate in the interview at a time and location most comfortable for them, thus protecting the privacy of the participant. During the consenting process, we will communicate with all participants that they have the right to download an audio and video recording of the interview. If the participant does not make this request, electronic copies of study data will be securely downloaded as two separate files (an audio-only and video recording file) to a local server from Zoom. Local video-files will be immediately deleted. The audio-only file will be immediately uploaded for storage on an online password-protected, backed up lab server that is accessible only by lab personnel. Local audio file copies will be deleted immediately once uploaded to the secure drive. The audio recording files will be labeled with a unique participant ID number, and will contain participants' voice but will not contain names. The labels on these files will constitute a link between identifiable information and the participant ID number, which will be used to link other study data together. Only members of the study team will be able to access the audio recordings taken during the interview session. Participant data will remain confidential. If the participant makes the request to have a personal copy of the interview, we will store the audio and video recording file in Zoom for one week, during which the participant will have one week to download and store the file using a secure Zoom link to the recording, sent via email. At the end of the one week the video recording will be downloaded such that audio file and video file are downloaded as separate files; the video file will be deleted immediately and will never be saved or stored. The audio-only file will be saved for transcription and immediately uploaded to the secure password-protected online lab server. Strict confidentiality will be maintained and all data will be coded by a subject number. Personal identifier records will be kept in a secure password-protected online server accessible only by research personnel. Any forms with identifying information will be stored separately from other study data. Records will be kept confidential to the level allowed by law and only the staff assigned to the study will have access to non-anonymous records. Information provided by study participants will not be released to outside sources unless written consent is provided by the study participant. Participants in the course will be made aware prior to consenting that participation involves a group Empowerment-Self Defense program where other participants will be present during physical training and group discussions. All program participants will be asked not to share any information about other program participants that may have come up during the program with anyone outside of the group. However, complete confidentiality cannot be guaranteed. For the interview administration, only the interviewer will be present in the private virtual call. Participants will receive a secure and private link to access the video-conferencing exit interview after course completion, which will restrict access to any users other than the participant and the single member of the research staff responsible for administering the interview. Research

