
a board comprising of; [name], [name], and [name] (Outlined in the Research Design tab). The DSMB is tasked with independently ensuring the safety of study participants and scientific goals. The DSMB will review the initial protocol and any proposed amendments, meet and complete reports quarterly, perform expedited monitoring of all serious adverse events, perform ongoing monitoring of drop-outs and non-serious adverse events, determine whether study procedures should be changed or the study should be halted for reasons related to the safety of study subjects, and perform periodic review of the completeness and validity of data to be used for analysis of safety and efficacy. The DSMB will also ensure subject privacy and research data confidentiality. A statistical penalty will not be assessed for the ongoing unblended review of safety by the DSMB. Unblinded data will not be released to investigators unless necessary for safety reasons. Suspected information security and privacy incidents will be reported within one hour to the DSM Board. Adverse Event (AE): Defined as any untoward medical occurrence in a patient or research subject administered a pharmaceutical product or other research intervention and that does not necessarily have a causal relationship with this treatment. An AE can therefore be any unfavorable and unintended sign (including an abnormal laboratory finding), symptom, or disease temporally associated with the use of a medicinal (investigational) product or research procedure, whether or not related to the medicinal (investigational) product or procedure. Negative events that occur during study involvement do not constitute adverse events unless they lead to physical harm (in which case the injury is the AE) or deterioration of mental health functioning (in which case the symptoms are the AE). Negative events that may potentially affect response to the intervention or study involvement should be reported as AEs. See IRB Reporting Requirements below for instructions on how to report these events. Examples might include legal problems or traumatic events. The program facilitator should query about adverse events (AEs) at every session by asking about any notable events since the last visit. These should be reviewed in a timely manner with the supervisor. Serious Adverse Event (SAE): An AE occurring in a patient or subject enrolled in a research study is serious if it results in any of the following outcomes: death, a life-threatening adverse drug experience, inpatient hospitalization or prolongation of existing hospitalization, a persistent or significant disability/incapacity, or is a congenital anomaly/birth defect.Unanticipated Problems Involving Risk (UPR): Defined as being (1) unexpected given the research procedures and characteristics of the population, (2) related (or possibly related) to participation in the research and (3) indicative that the research may place the subject or others at a greater risk of harm than was previously known. Examples of possible UPRs for psychotherapeutic interventions: 1. Psychosis or mania2. New onset or clinically significant exacerbation of a psychiatric disorder3. Suicide and suicide attemptsAn incident, experience, or outcome that meets UPR criteria generally will warrant consideration of substantive changes in the research protocol or informed consent process/ document or other corrective actions in order to protect the safety, welfare, or rights of subjects or others. Examples of corrective actions or substantive changes that might need to be considered in response to an unanticipated problem include: modification of inclusion or exclusion criteria to mitigate the newly identified risks; implementation of additional procedures for monitoring subjects; suspension of enrollment of new subjects; suspension of research procedures in currently enrolled subjects: modification of informed consent documents to include a description of newly recognized risks; and provision of additional information about newly recognized risks to previously enrolled subjects. Reporting Requirement: All UPRs/AEs/SAEs, regardless of relatedness to the intervention, are to be reported to the local IRB as soon as possible, no later than 10 business days from the date the investigator or research staff becomes aware of the event/problem. Fill out an AE form, SAE form, and/or UPR form, obtain the study PI's signature, and submit to the Hunter IRB. Then forward each AE/SAE/UPR form to Data Safety Monitoring Board as soon as possible. The study PI will maintain a record of all AEs/SAEs/UPRs to report to the Hunter IRB in summary or table form at the end of the study. The PI will notify NIMHD of any UPR, AE, or SAE promptly via email. Protocol Deviation/ViolationA protocol deviation or violation is any change, divergence, or departure from the study design or procedures of a research protocol. Investigators are required to conduct their research according to the plans reviewed and approved by the IRB. Instances where this does not occur, either inadvertently due to circumstances beyond the investigator's control, or due to errors of omission or commission by research project staff, must be reported. Reporting Requirement: Fill out a Protocol Deviation/Violation form, and submit to local IRB within 3 days of the occurrence (one day if there was harm to the participant). Also email the form (with encryption) to the PI and Study Coordinator, who will maintain a record of all Protocol Deviations/Violations to report to the Hunter IRB.

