Data Management. Following the CONSORT statement,⁸² we will track how many participants: (a) are told about the study; (b) are screened for the study; (c) do and do not meet inclusion criteria; (d) are invited to participate; and (e) actually enroll. Pre-inclusion attrition rates may reveal potential enrollment bias. To explore how differential refusal may affect generalizability of findings, we will also record the reasons for exclusion from and refusal to participate in the study. As recommended by the IOM Report,⁸³ we will model the effects of dropout patterns as data not missing at random using Bayesian analysis utilizing a pattern-mixture modeling approach. We will consider scale transformations, such as log, to decrease the effect of outliers.

Feasibility Analyses. The primary target outcomes of Aim 2 will be completion of the pilot study at the target recruitment total (n = 48), with < 25% dropout from assessments (Table 1. Research Plan). Secondary target outcomes related to assessment procedures, acceptability of the intervention, and laboratory and data management are detailed in Table 1 of the Research Plan. Successful completion of the pilot trial, including meeting or exceeding these benchmarks for success, will support the feasibility and acceptability of recruiting participants into a future RCT of the tailored ESD intervention using similar procedures and a similar population.

Power Analyses. Preliminary efficacy of the tailored ESD violence prevention intervention will be evaluated as an exploratory aim via administration of the battery of validated questionnaires assessing 1) behavior change variables (i.e., use of resistance tactics, self-protective behavior, and assertive relational communication); 2) psychological variables hypothesized to mediate the effects of the intervention on behavior (i.e., resistance self-efficacy, attributions of self-blame, rape myth acceptance, gender minority risk and resilience factors); and 3) reductions in rates of exposure to victimization) at baseline, post-intervention, and at the 3- and 6-month follow-up assessments.

Given its modest size and aims, this pilot is not powered to detect reductions in victimization exposure. Nonetheless, we will conduct exploratory analyses to evaluate potential trends that may emerge for the effects of treatment on behavior change, violence risk and resilience variables, and victimization.

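### In the documents provided, adverse events are solicited only at the five course sessions; for about 84% to 87% of calendar time to 6 months, recording depends on staff happening to learn of them

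*Protocol*

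**What the plan says.** The AE text in Protocol Section 7 stands under the headings for stopping rules and discontinuation criteria, is repeated for the DSMB entries, and appears again in Section 16. Its only instruction for eliciting events is: "The program facilitator should query about adverse events (AEs) at every session by asking about any notable events since the last visit". The facilitator's contact with participants is the course itself, given "in a 20-hour training program, in 5 4-hour sessions" (Section 5).

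The contacts after that are:

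- **Surveys.** Section 6 states: "Self-report questionnaires will be administered to each participant 3 times; baseline, follow-up immediately following course completion, and 6-month follow-up". Section 16 adds: "The 6 month follow-up survey must be completed remotely".
- **Exit interview.** Section 6 says that it "will take place in the weeks immediately following the course".

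Neither is described as asking about AEs.

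The AE definition is wider than the classroom. A negative event during study involvement counts when it leads to physical injury or worsening mental health, and legal problems and traumatic events are given as examples to report. Reporting to the IRB is due within 10 business days of staff becoming aware, with forms then sent to the DSMB. No end date is set. Section 16 also asks the DSMB to "perform ongoing monitoring of drop-outs and non-serious adverse events".

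The SAP has no safety analysis. Its Power Analyses paragraph places the efficacy questionnaires "at baseline, post-intervention, and at the 3- and 6-month follow-up assessments".

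**The concern.** The definition and the method of ascertainment cover different periods. The definition runs for as long as a woman is in the study. The question that would find events runs until her last attended session. After that, an injury or a legal problem enters the record only if she volunteers it or a staff member happens to learn of it.

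This matters because a stated aim (Section 5) is greater use of resistance strategies, and participants would use those in their own lives, largely after the course. The follow-up months are where consequences of that use could be learned about, and they would inform the planned RCT. Solicited and volunteered counts are not comparable. An AE table that merges them would make follow-up look quieter than the course simply because nobody asked.

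**Working it through.** The plan states no figure for AE coverage, so there is none to reproduce. The check has two parts.

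**1. Where an AE question is asked**

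| Contact | Source | AE question described? |
|---|---|---|
| Five sessions | Sections 7 and 16 | Yes, by the facilitator |
| Post-course survey | Sections 5 and 6 | No; instruments listed by title, none an AE form |
| Exit interview | Section 6 | No; questions are in an attachment not provided |
| 3-month assessment | SAP only | No; named for efficacy variables |
| 6-month survey, remote | Sections 6 and 16 | No; same listed battery |

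The battery in Section 5 does include the Sexual Experiences Survey, Conflict Tactics Scale, PCL-5, Depression Anxiety and Stress Scale and Resistance Tactics Survey. These are outcome measures, and no text turns a response into an AE form. Section 6 provides counselling referral for distress, which is a care route and not AE recording.

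**2. How much calendar time the question covers**

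Inputs: session dates in Section 6, with the 6-month point taken as six calendar months after the last session.

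Covered share = (last session − first session) / (6-month point − first session).

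| Series | First to last session | Covered days | Last session to 6 months | Covered | Not covered |
|---|---|---|---|---|---|
| 1 | 7/11/21 to 8/8/21 | 28 | 184 days (to 2/8/22) | 28/212 = 13.2% | 184/212 = 86.8% |
| 2 | 9/19/21 to 10/17/21 | 28 | 182 days (to 4/17/22) | 28/210 = 13.3% | 182/210 = 86.7% |
| 3 | 11/14/21 to 12/19/21 | 35 | 182 days (to 6/19/22) | 35/217 = 16.1% | 182/217 = 83.9% |
| All | | 91 | 548 | 91/639 = 14.2% | 548/639 = 85.8% |

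These shares are for a woman who attends every session. The first two sessions are 7 days apart in each series. A woman who stops after session 2 is therefore covered for 7/212 = 3.3% of the time in series 1, and is unsolicited for the other 96.7%.

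**Illustration under an assumed rate.** The documents give no AE rate. If each woman independently had 6-month risk p, the chance of at least one event among n women is 1 − (1 − p)^n. The table uses the target of 48, and 36 = 0.75 × 48 at the dropout benchmark.

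| p (assumed) | Expected women with an event, n = 48 | Chance of at least one, n = 48 | Chance of at least one, n = 36 |
|---|---|---|---|
| 1% | 0.48 | 0.383 | 0.304 |
| 2% | 0.96 | 0.621 | 0.517 |
| 5% | 2.4 | 0.915 | 0.842 |
| 10% | 4.8 | 0.994 | 0.977 |

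At an assumed risk of 2% or more, at least one follow-up event is more likely than not, and the text as written would solicit none of them.

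**The case against.** Several stronger readings are tempting, and the documents do not support them.

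- **That follow-up events would go uncounted.** Section 7 obliges staff to report every AE they learn of, related or not, with no end date. An injury mentioned in an interview or in a survey that staff read falls under that duty. What is missing is active solicitation and a procedure from disclosure to report.
- **That nothing at all is asked after session 5.** The survey battery, course forms and interview questions are in an assessment packet not provided. The listed instruments show no AE form, but an item inside the packet cannot be excluded.
- **That all dropouts are lost to safety follow-up.** Section 15 separates leaving the course from leaving the research and pays for questionnaires either way. Women who leave are also queried up to their last attended session.
- **That follow-up is the main risk period.** No document gives an injury rate or says that resistance raises harm; the Lay Summary says that it deters rape. Injuries in physical drills would occur in sessions, where the query operates. The 84% to 87% is a share of time, not of risk.
- **That a clean AE table would be used to bound a harm rate.** Neither document plans a safety rate or a safety conclusion. Aim 2 concerns feasibility and acceptability.

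It is also fair that 6-month answers could not alter delivery here. Series 1 reaches 6 months on 2/8/22, after series 3 ends on 12/19/21. Post-course and interview answers could, because series 2 starts 42 days after series 1 ends, and series 3 starts 28 days after series 2 ends.

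What stands is the mismatch: a study-long definition, a question that stops at the last attended session, and passive awareness after it.

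**Conclusion.** The point holds as a gap in ascertainment and should be corrected. It does not undermine the feasibility aims. The text provided solicits AEs for 28 to 35 days per series and leaves 83.9% to 86.8% of calendar time to 6 months unsolicited, and more for women who stop attending early.

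This rests on three assumptions: the sessions ran on the listed dates, follow-up is six calendar months from the last session, and the unseen packet holds no AE item. If it does hold one, the point narrows to the missing route from a response to an AE report. That follow-up matters for harm is an inference from the course's aim, not a figure in the documents.

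**What to change.** 1. Put the same AE question in the post-course survey, the exit interview and the 6-month survey, each asking about the time since the last contact and naming injury or other consequences when resisting. Send it also to women who left the course but not the research.
2. Have staff review answers promptly. Section 16 has surveys submitted without identifiers and contact sheets held separately, so state how a positive answer is linked by participant ID to the contact sheet. File positives on the existing AE form to the IRB and DSMB.
3. Report AEs separately for the course (solicited at sessions) and for follow-up, stating how each was ascertained. Do not present follow-up as event-free where it was not queried.
4. Reconcile the SAP's 3-month assessment with the protocol's schedule, which has none, when placing the question.

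**Cost.** A small amendment, staff review of up to 48 responses per contact, a linkage step and possibly consent wording. Surveys are optional, so the change reaches responders only.

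**Timing.** The planned 6-month points (2/8/22 to 6/19/22) precede the SAP date of 1/18/2023. If that schedule held, only the reporting step can still be applied here, and the question itself belongs in the future RCT.
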